### 1051 **7.2.4 Endothelial Cell Density (ECD)**

#### 1052 **7.2.4.1 Included Subjects**

1053 The primary analysis will include all study participants with a gradable 3-year image, who have  
1054 not experienced graft failure 3 years after transplantation. Study participants with a missing cell  
1055 count at 3 years will be included in a secondary analysis using Rubin's method of multiple  
1056 imputation.

1057

#### 1058 **7.2.4.2 Outcome Measures**

1059 The primary outcome will be the ECD at 3 years, conditional on graft survival at 3 years. All  
1060 other ECD measurements during follow up will be considered as a secondary outcome.

1061

#### 1062 **7.2.4.3 Descriptive Statistics**

- 1063 • Summary statistics (mean  $\pm$  SD and/or median/quartiles as appropriate to the distribution)  
1064 will be given for the ECD by the 2 treatment groups ( $\leq 7$  and 8 to 14 days) and 4 treatment  
1065 groups (0 – 4, 5 – 7, 8 – 11, and 12 – 14 days).
- 1066 • Change from eye bank determined screening ECD will be summarized in a similar manner.
- 1067 • Boxplots of ECD and change from eye bank determined screening ECD will be given for the  
1068 2 randomization groups.
- 1069 • A scatter plot will be constructed of eye bank determined screening ECD vs. 3 year ECD  
1070 with a symbol used to denote the two randomization groups.

1071

#### 1072 **7.2.4.4 Primary Analysis**

1073 The primary analysis will be limited to subjects with gradable 3 year images, who have not  
1074 experienced graft failure 3 years after transplantation. An ANCOVA model with 3 year ECD as  
1075 the dependent variable adjusting for eye-bank-determined screening ECD will be used to assess  
1076 the effect of preservation time. The time from preservation to surgery will be treated as a binary

1077 variable. If residual values from the models above are highly skewed then a transformation (e.g.,  
1078 square root or logarithm) or non-parametric methods will be used instead.

1079 • Random effects will be modeled to account for any correlated data from the same donor and  
1080 any correlated data from 2 study eyes of the same study participant.  
1081 • Additional ANCOVA models will also adjust for other recipient/donor risk factors, (if  $p <$   
1082 0.05. Random surgeon effects will also be explored using a mixed effects model.

1083

#### 1084 **7.2.4.5 Secondary Analyses**

##### 1085 **7.2.4.5.1 Sensitivity Analysis**

1086 Sensitivity analysis will also be performed to check whether results change meaningfully  
1087 depending on how missing data are handled. The missing 3 year ECD values for subjects with  
1088 surviving grafts at 3 years will be imputed and included in an analysis as described in the  
1089 previous section. The data imputation will be performed by using Rubin's method of multiple  
1090 imputation.

1091

##### 1092

##### 1093 **7.2.4.5.2 Analysis with donor tissue preservation time as continuous/multi-categorical**

1094 **variable**

1095 The analyses described above will be repeated with time from preservation to surgery treated as  
1096 continuous (using time of day to calculate hours from preservation to surgery) or multi-category  
1097 variable (0 – 4, 5 – 7, 8 – 11, and 12 – 14 days from preservation to surgery) in separate models.

1098

##### 1099 **7.2.4.5.3 Longitudinal analysis**

1100 This analysis also will be limited to subjects with a surviving graft at 3 years. A repeated  
1101 measures least squares regression model will be fit using all available images at baseline, 6  
1102 months, 1, 2, and 3 years. This analysis will be performed *with* and *without* imputation of  
1103 missing data. Rubin's method of data imputation will be used to impute the ECD values for all  
1104 missing time points. The time from preservation to surgery will be modeled as both continuous  
1105 and categorical as described above. If residual values have a skewed distribution then  
1106 transformation (e.g., square root or logarithm) or non-parametric analysis will be used.

1107

#### 1108 **7.2.5 Course of Cornea Changes After Endothelial Keratoplasty**

1109 The association of donor, operative and postoperative related factors with ECD will be evaluated  
1110 and assessed in univariate and multivariate ANCOVA models , adjusting for the reading center  
1111 grading of pre-operative ECD (imaged post-cut if the eye bank was performing the cutting and  
1112 imaged just prior to shipping if the surgeon was performing the cutting). This ECD value will be  
1113 considered the baseline for these analyses.

1114

#### 1115 **7.2.6 Safety Analysis Plan**

1116 The main safety analysis will involve tabulation of data by treatment group of events that could  
1117 be considered possibly related to the preservation time such as post-op infection. The efficacy  
1118 analyses related to graft failure, corneal thickness, and ECDs also could be viewed as safety  
1119 analyses. Operative and post-operative complications will also be tabulated.

1120  
1121 Further details of the analytic approach will be provided in the detailed statistical analysis plan.

1122 **7.2.7 Additional Tabulations and Analyses**

1123 The following will be tabulated according to treatment group:

1124 • Baseline demographic and clinical characteristics  
1125 • Visit completion rate for each visit  
1126 • Protocol deviations

1127

1128 **7.2.8 DSMC Interim Analysis Plan**

1129 No formal interim analyses are planned towards demonstrating non-inferiority before the end of  
1130 the study since the recruitment period is planned to be short compared with the follow-up period  
1131 and since we believe it is imperative to have three years of follow up to assess non-inferiority.

1132 .

1133 In addition to semi-annual review described in Section 5.2, the following plan for interim  
1134 monitoring for a potential recommendation of early stopping of enrollment has been established  
1135 in conjunction with the DSMC. This plan is based on early donor failure rate and on the  
1136 progress of recruitment.

- 1137 • Rate of failure within the first 8 weeks: Upon enrollment of the first 100 eyes, and then  
1138 quarterly thereafter (i.e., one review between each DSMC semi-annual meeting) the  
1139 DMAC will evaluate the failure rate within the first 8 weeks (i.e. both the early failures  
1140 and the primary donor failures, as defined in Section 4.6) in each group and notify the  
1141 DSMC who will have the option of requesting additional information between the semi-  
1142 annual reviews. The DSMC may also request more frequent reviews at any time.
- 1143 • Recruitment Progress: Recruitment progress will be evaluated at the first two DSMC  
1144 meetings following initiation of recruitment. If based on the current recruitment total  
1145 and recruitment trend over the previous 3 months, the projected timeline for the  
1146 remaining recruitment is more than 16 months at the 1st review or more than 12 months at  
1147 the 2nd review, the DSMC will discuss whether the study timeline can be met.

1148 Following each DSMC data review, a summary will be provided to the IRBs.

1149  
1150

1151

1152  
1153  
1154  
1155

## APPENDIX A

## PROTOCOL AMENDMENT #1

## EXTENSION OF FOLLOW-UP TO COMMON END DATE

July 1, 2015

1229 **1. Overview: Extension of follow-up after 3 years.**

1230 Participants who re-consent to additional follow-up will continue annual protocol visits  
1231 past the 3-year time point, until at least 2017. The same data will be captured from annual visits  
1232 as well as interim unscheduled visits as was done previously. The same study specific tests –  
1233 pachymetry and specular/confocal microscopy - will continue to be performed at the annual  
1234 visits. Visits will continue to be captured until approximately the 2nd quarter of 2017, therefore  
1235 all participants will have a last possible common endpoint rather than exiting individually when  
1236 they reach their 3 year post-operative visit.

1237 *Rationale: Continued follow-up of CPTS participants provides an excellent opportunity to  
1238 gain more information about many factors affecting DSAEK outcomes, including donor age  
1239 and preservation time. This additional longitudinal data will provide important information  
1240 on longer term DSAEK outcomes that are not necessarily impacted by preservation time,  
1241 although we will continue to assess that variable as well.*

1242

1243 **2. Eligibility and Informed Consent**

1244 **a. Eligibility**

1245 All active study participants will be eligible for extended follow-up to a common end date, until  
1246 at least 2017. The exact end date will be determined by the Operations Committee based on  
1247 funding and data analysis requirements.

1248 **b. Informed Consent**

1249 Active study participants will be asked to sign a new informed consent form or addendum prior  
1250 to the post-3 year visits or as soon thereafter as feasible. The new informed consent form (or  
1251 addendum) may be signed during the next scheduled visit (either Protocol Visit or Unspecified  
1252 Visit) or by mail if the governing IRB approves that process. Until the new informed consent  
1253 form or addendum is signed, the study participant will not be examined post-3 year for study  
1254 purposes. If the new informed consent form or addendum is not signed, follow-up for that  
1255 participant will end upon completion of the 36-month visit.

1256 **3. Follow-Up Visits**

1257 **a. Visit Schedule and Windows**

1258 The post-3 year visit schedule will vary by the participant's enrollment date. Some participants  
1259 will be eligible for Year 4 and Year 5 visits if the windows below fall within the extended  
1260 follow-up period.

1261 Additional protocol-specified follow-up visits (and visit windows) for the first eye, will be as  
1262 follows:

- 1263 • 48 months (44 - 52 months)
- 1264 • 60 months (56 – 64 months)

1268 Additional visits may be performed more often as needed. A data form will be completed for  
1269 each protocol visit and any non-protocol visits where the intent of the visit was to examine the  
1270 study eye by a study investigator. Additional non-protocol visits by non-study investigators may  
1271 also be uploaded by the clinical site to the study website, as was done during the initial 3-year  
1272 follow-up phase. For example, if graft failure is determined and a regraft is required on a non-  
1273 protocol visit, the appropriate follow-up visit form and graft failure form should be completed if  
1274 and when this occurs.

1275 If the second eye of an active participant was enrolled, a modified visit schedule will be  
1276 allowed to minimize return visits for participants that had bilateral EK as part of the study. For  
1277 example, sites will be allowed to follow standard of care practices to avoid unnecessary visits  
1278 linked to targeting each eye within its respective windows as listed above. Sites are encouraged  
1279 to schedule both eyes within their respective windows when the windows overlap, but at  
1280 minimum at least one eye must be within its target visit window at each visit.

1281  
1282 **b. Testing Procedures**  
1283 The Table below shows the key elements of data collection at each study visit. Additional  
1284 visits may occur as needed for the usual care of the participant.

1285

	48 Months	60 Months
Parameters		
Medication History	X	X
Slit lamp examination	X	X
Intraocular pressure	X	X
Ultrasonic pachymetry	X	X
Endothelial imaging	X	X
Post-op complications and other untoward events	X	X

1295  
1296  
1297 **c. Detailed Testing Procedures**  
1298 Procedures for testing at each follow-up visit are identical as listed in Chapter 4.

1300  
1301 **d. Adverse Events**  
1302 Adverse event reporting remains identical to Chapter 5.

1303  
1304 **e. Other Considerations in Follow-up**  
1305 All other retention and follow-up procedures including central contract from the  
Coordinating Center will continue as in the original study and as outlined in Chapter 6.

1306

1307 **4. Statistical Analyses**

1308 The statistical methods for all 3 study objectives completed up to the 3 year primary endpoint  
1309 will be extended to the 4 and 5 year endpoints. Additional analyses on the impact of missing  
1310 data will be evaluated, including comparison of baseline characteristics for those who agreed  
1311 versus declined to consent to continue .

1312

1313

1314

1315

1316

1317

1318

1319

1320

1321

1  
2  
3

## Version History

Version Number	Author	Approver	Effective Date	Revision Description
1.0	[name]	[name]	9-4-14	Revisions prior to 9-4-14 were not versioned according to new JCHR standards. Changes were clarifications from DSMC meetings and were documented in DSMC meeting minutes.
2.0	[name]	[name]	8-12-15	Added analyses related to extension of CPTS to capture 4 and 5 year visits, which was incorporated into protocol version 4.0.
3.0	[name]	[name]	1-15-16	The DSMC, OC, and EC approved the clarification of how to handle cases that were cloudy at the 3 year visit. Details of the original discussion are in the November 3, 2015 DSMC minutes and details of the discussion/proposal that followed (and final decision) are in the following folder: Analysis Notes to Save\3 year failure cutoff discussions
4.0	[name]	[name]	6-21-16	
 
1. Clarify that “surgical trauma” (like blunt and penetrating trauma) is also a severe event, if leading to failure, that is unrelated to PT and should be censored prior to the event.
 
2. Clarify that out of window 3 year visits can be used up to 44 months for determining 3 year failures. Decision/discussion saved in the following folder: Analysis Notes to Save\3 year visit window
 

13

# CPTS Statistical Analysis Plan

## 1.0 Study Objectives

17 The objectives of the “Effect of Corneal Preservation Time on Long-Term Graft Success” (CPTS)  
18 study are:

20 Objective 1 (Primary Objective): To determine if the 3-year graft failure rate following EK  
21 performed with donor corneas with a preservation time of 8 to 14 days is non-inferior to the  
22 failure rate when donor corneas with a preservation time of 7 or fewer days are used.

24 Objective 2: To determine if the central corneal endothelial cell density 3-years after EK is  
25 related to preservation time.

27 Objective 3: To evaluate the effect of donor, operative and postoperative factors on graft  
28 failure and endothelial cell density three years following EK.

30 The purpose of this document is to describe the analysis plan for these 3 objectives, as well as some  
31 pre-planned secondary analyses. There may be additional secondary analyses performed that are not  
32 described in this document.

## 2.0 Sample Size

35 The sample size of 1330 is calculated based on a non-inferiority (a single one-sided test) design with  
36 the goal to determine that the graft failure rate of the recipients of donor tissue transplanted 8 to 14  
37 days after preservation is not worse than the graft failure rate of recipients of donor tissue transplanted  
38  $\leq$  7 days after preservation.

Non-Inferiority Limit	Power = 90 %				
	Failure Rate				
	12 %	10 %	8 % a	6 %	4 %
10 %	362	310			
8 %	566	482	394		
6 %	1006	858	702	538	
4 %	2262	1928	1576	1208	824
2 %	9044	7708	6304	4832	3290

40 Note: Numbers in table are total sample size for both treatment groups combined  
41 (crossover and lost to follow up are not accounted for). Half would be randomized to  
42 each group.

43 a CDS data: 3-year failure rate

45 In the Cornea Donor Study (CDS), the 3-year failure rate was 8%. Clinical expectations suggest that  
46 the graft failure rate from the EK procedure will be smaller than the failure rate from the PKP  
47 procedure that was used in CDS; therefore, a 3-year failure rate of 6% has been assumed. Based on  
48 equal allocation of recipients to each group and type I error of 5%, a sample size of 1208 will provide  
49 90% power for a non-inferiority limit of 4%. Based on information from the CDS, approximately  
50 10% of subjects will have incomplete follow up (due to death, withdrawal or lost to follow up) by the  
51 end of year 3. Increasing the calculated sample size by this amount gives a total of 1330 subjects  
52 (665 per group).

53 • The inclusion of participants with two study eyes, one in each treatment group, will tend to  
54 reduce the variance and as a result increase statistical power. To be conservative, this has not

55  
56  
57  
58  
59 been accounted for in the sample size estimation, since the correlation of outcome with two  
56 eyes is not known.  
57  
58

## 59 **3.0 Graft Failure (Primary Outcome)**

### 60 **3.1 Primary Analysis of 3 Year Graft Failure - (Analysis plan for objective 1)**

#### 61 **3.1.1 Formal Statistical Hypothesis**

62  
63 The primary objective of the study is to determine if the 3-year graft failure rate  
64 following EK performed with donor corneas with a preservation time of 8 to 14 days  
65 is non-inferior to the failure rate when donor corneas with a preservation time of 7 or  
66 fewer days are used. In terms of formal statistical hypothesis testing, the null and  
67 alternative hypotheses are:  
68

69  
70  $H_0: p_{8-14} - p_{0-7} \geq 4\%$   
71  $H_a: p_{8-14} - p_{0-7} < 4\%$   
72

73 where  $p_{8-14}$  and  $p_{0-7}$  is the probability of graft failure by 3 years in the 8-14 day group  
74 and the  $\leq 7$  day group, respectively.  
75

#### 76 **3.1.2 Analysis Cohort**

77 Participant study eyes that did not have surgery, received a non-study donor, had an  
78 AC IOL implanted during surgery, or experienced a suprachoroidal hemorrhage will  
79 be excluded from the primary analysis. It is highly unlikely these events could be  
80 related to preservation time, thus inclusion of them could actually bias *towards*  
81 concluding non-inferiority. Therefore, the primary analysis will deviate from the  
82 principle of intent-to-treat, but this approach is conservative for a non-inferiority  
83 analysis.  
84

#### 85 **3.1.2.1 Censoring of Data for Occurrence of a Severe Event Unrelated to 86 Preservation Time**

87 In order to minimize bias towards concluding non-inferiority, severe events  
88 not expected to be related to preservation time will be censored at the last  
89 examination prior to the occurrence of the event that severely impacts the study  
90 eye, if the eye was not on the path to failure at the last visit prior to the  
91 occurrence of the severe unrelated event (see 3.1.5 for the 'rules'). These  
92 events include:  
93

- 94 ▪ Enucleation (eye will be dropped)
- 95 ▪ Phthisis (eye will be dropped)
- 96 ▪ Failure due to surgical (unrelated to the initial DSEK), blunt or  
97 penetrating trauma (eye will be followed until failure criteria met)

#### 98 **3.1.2.2 Analyzing Preservation Time Group Crossovers As-Treated**

99 If a study eye receives a study donor cornea in the wrong preservation time  
100 group, it will be analyzed as treated, as this will minimize bias towards  
101 concluding non-inferiority. A secondary intent-to-treat analysis will also be  
102 completed if this occurs.  
103

104  
105  
106  
107  
108  
109  
110  
111  
112  
113  
114  
115  
116  
117  
118  
119  
120  
121  
122  
123  
124  
125  
126  
127  
128  
129  
130  
131  
132  
133  
134  
135  
136  
137  
138  
139  
140  
141  
142  
143  
144  
145  
146  
147  
148  
149  
150  
151  
152

### 3.1.3 Definition of Graft Failure (per protocol, section 4.7):

Graft failure will be assessed and defined as the occurrence of one of the following:

- Cornea which requires regrafting for any reason
- Cornea which remains cloudy without clearing, according to the following:
  - (1) cloudy cornea on the first postoperative day which does not clear within 8 weeks  
OR
  - (2) cloudy cornea which was initially clear postoperatively but becomes and remains cloudy for 3 months without clearing.

*Note: graft failure is based on cloudy recipient stroma. Any reference to cloudy cornea when defining graft failure is with regard to the recipient stromal clarity.*

For eyes meeting the definition of graft failure above, the principal cause of graft failure will be classified as one of the following:

- Early failure (cloudy or equivocal recipient cornea on the first postoperative day which does not clear or requires a regraft within 8 weeks), associated with surgical complications, including immediate peri-operative complications such as acute angle closure noted on the 1 day post-operative visit
- Primary donor failure (cloudy or equivocal recipient cornea on the first postoperative day which does not clear or requires a regraft within 8 weeks), in the absence of surgical complications
- Graft rejection (defined as a clouded recipient central stroma following an allograft reaction);
- Non-rejection graft failure (defined as a graft that initially had a clear central recipient stroma and becomes cloudy due to causes other than an immune event. These include: surface failure, infection, glaucoma/hypotony, endothelial decompensation, interface irregularity or opacity, pre-existing stromal scarring, blunt or penetrating trauma, and other causes);
- Refractive/visual graft failure (defined as a graft that requires regrafting due to inadequate vision while the recipient central stroma remains clear).

### 3.1.4 Definition of Graft Failure Date

A cornea that is “on the path to failure” means the cornea has met criteria to initiate the path to failure and it has not been removed from that path, defined as follows:

1. Definition of how to initiate “on the path to failure” :
  - Initiating At 1 Day Visit: A cornea may be classified as either cloudy or equivocally cloudy to start a count of how many days “on the path to failure”.
  - Initiating After 1 Day Visit: A cornea must be initially classified as cloudy to start a count of how many days “on the path to failure”.
2. A cornea classified as equivocal after the “on the path to failure” count begins is still considered “on the path to failure.”
3. A cornea classified as clear after the “on the path to failure” count begins is no longer “on the path to failure”; the count restarts the next time the cornea is classified as cloudy.

The date of graft failure is defined as follows

153  
154 1. If “on the path to failure” (per 3.1.4 above) initiates at the 1 Day Visit:  
155 a. If the cornea remains “on the path to failure” (per 3.1.4 above), is  
156 classified cloudy at least once during those consecutive visits, and is  
157 classified cloudy at least 56 days after surgery date, then the cornea meets  
158 the failure definition and the date of failure will be the date of the 1 day  
159 visit. (Note: this means it must be classified cloudy at least twice during  
160 the path to failure, and at least one of those  $\geq 56$  days after surgery)  
161 b. If the cornea remains “on the path to failure” (per 3.1.4 above) and a  
162 regraft occurs within 56 days or after 56 days (but prior to being classified  
163 cloudy after 56 days), the date of failure will equal the date of the 1 day  
visit.  
164 2. If “on the path to failure” (per 3.1.4 above) initiates after the 1 Day Visit:  
165 a. If a cornea is classified as cloudy, remains “on the path to failure” (per  
166 3.1.4 above), and is classified cloudy at least 90 days after the initial  
167 cloudy classification, then the cornea meets the failure definition and the  
168 date of failure will be the first date at which cornea is indicated as cloudy.  
169 b. If a cornea is “on the path to failure” (per 3.1.4 above) for  $<90$  days and a  
170 regraft occurs, the date of failure will equal the first exam date where the  
171 cornea is cloudy.  
172 3. If a cornea is clear and then a regraft occurs, the date of failure will be equal to  
173 the date of regraft.

174  
175 Examples

176 Example 1  
177 equivocal (1 day) ← failure date  
178 equivocal  
179 cloudy (>56 days after surgery)  
180 cloudy (need the second cloudy to confirm)

181 Example 2  
182 equivocal (1 day) ← failure date  
183 equivocal  
184 regraft

185 Example 3  
186 clear  
187 equivocal  
188 cloudy\* ← failure date  
189 equivocal  
190 cloudy (>90 days after \*)

191 Example 4  
192 clear  
193 cloudy  
194 clear  
195 cloudy\* ← failure date  
196 cloudy (<90 days after \*)  
197 regraft

198 Example 5  
199 clear  
200 clear  
201 regraft ← failure date  
202  
203  
204  
205  
206  
207

208  
209  
210  
211  
212  
213  
214  
215  
216  
217  
218  
219  
220  
221  
222  
223  
224

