#### 699       **4.7 Graft Failure**

700       Graft failure will be assessed and defined as the occurrence of one of the following:

701       • Cornea which requires regrafting for any reason  
702       • Cornea which remains cloudy without clearing, according to the following:  
703           (1) cloudy cornea on the first postoperative day which does not clear within 8 weeks  
704           OR  
705           (2) cloudy cornea which was initially clear postoperatively but becomes and remains  
706           cloudy for 3 months without clearing.  
707           ■ *A study participant whose cornea becomes cloudy (clouded recipient  
708           central stroma, based on the modified CDS grading scale) will be treated  
709           by the investigator's usual routine.*

710       For eyes meeting the definition of graft failure above, the principal cause of graft failure will be  
711       classified as one of the following:

712       • Early failure (cloudy cornea on the first postoperative day which does not clear or  
713       requires a regraft within 8 weeks), associated with surgical complications  
714       • Primary donor failure (cloudy cornea on the first postoperative day which does not  
715       clear or requires a regraft within 8 weeks), in the absence of surgical complications  
716       • Graft rejection (defined as a clouded recipient central stroma following an allograft  
717       reaction);  
718       • Non-rejection graft failure (defined as a graft that initially had a clear central recipient  
719       stroma and becomes cloudy due to causes other than an immune event. These include:  
720       surface failure, infection, glaucoma/hypotony, endothelial decompensation, interface  
721       irregularity or opacity, pre-existing stromal scarring, blunt or penetrating trauma, and  
722       other causes);

723       • Refractive/visual graft failure (defined as a graft that requires regrafting due to  
724           inadequate vision while the recipient central stroma remains clear).

725

726

727 **4.8 Final Status**

728 A Participant Final Status Form will be completed if the participant dies, withdraws, or is  
729 deemed to be lost to follow-up by the CC staff. An Eye Final Status Form will be completed if a  
730 study eye is re-grafted, receives an AC IOL during surgery, experiences a suprachoroidal  
731 hemorrhage during surgery, receives a non-study donor cornea, will no longer have surgery, or  

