#### 3.1.5.2 Eyes with 3 Year Visit Not Meeting Failure Criteria

In eyes that complete the 3 year visit without meeting criteria for graft failure the following ‘rules’ will apply:

1. If the cornea is “on the path to failure” (per 3.1.4 above) at the 3 year visit, data beyond the 3 year visit up to 42 months will be used (if available) to determine whether the cornea will be considered a failure up to 3 years. Data beyond 42 months will not be used for this assessment.
  - If the cornea clears at a subsequent follow-up visit (within 42 months) prior to meeting confirmation of failure criteria, the cornea will not be classified as a graft failure and data will be censored at the 3 year visit.
  - If additional follow-up data (within 42 months) confirm a failure (via regraft or 90 days confirmed cloudy), then the cornea will be classified as a graft failure up to 3 years and date of failure will be determined per 3.1.4 above.
  - If data beyond the 3 year visit are not available, OR the cornea remains “on the path to failure” beyond the 3 year visit but the follow-up data that are available within 42 months still do not confirm failure, the case will be flagged for **‘non-protocol’ graft failure review by the Executive Committee**. (Note all of these cases will have been cloudy at least once during the “on the path to failure” period.) If confirmed as a non-protocol graft failure, the failure date will be determined per 3.1.4 above.
2. If the cornea is not “on the path to failure” (clear or equivocal following clear) at the 3 year visit, it *will NOT* be considered a graft failure and the data will be **censored** at the 3 year visit

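### SAP 3.1.4 sets no end to the day-1 failure path for an eye graded only equivocal on day 1, and SAP 3.1.5 then treats the same history in two ways

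*Combined protocol and SAP*

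**What the plan says.** SAP 3.1.4 opens the path at the first visit in these terms: "Initiating At 1 Day Visit: A cornea may be classified as either cloudy or equivocally cloudy to start a count of how many days" the eye has been on it. After day 1 only a cloudy grade can open it. Point 2 of the same list reads "A cornea classified as equivocal after the" count has begun, and keeps such an eye on the path. A clear grade is the only exit.

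For a path that opens on day 1:

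- Rule 1a: an eye still on the path that is "classified cloudy at least 56 days after surgery date, then the cornea meets" the definition of failure. A bracketed note requires two cloudy grades in all, at least one of them on or after day 56. The date is the day-1 visit.
- Rule 1b: the date is also the day-1 visit where a "regraft occurs within 56 days or after 56 days (but prior to being classified" cloudy after that day.

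For a path that opens later, rule 2 requires a cloudy grade at least 90 days after the first one, or a regraft, and dates the failure to that first cloudy grade.

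Protocol 4.7, repeated in SAP 3.1.3, gives two clouding routes. One is a cornea cloudy on day 1 that has not cleared by 8 weeks. The other is a "cloudy cornea which was initially clear postoperatively but becomes and remains" cloudy for 3 months. Protocol 4.5.1.1 makes equivocal a separate grade from clouded. The cause list in SAP 3.1.3 does admit equivocal eyes: "Primary donor failure (cloudy or equivocal recipient cornea on the first postoperative day which does not clear or requires a regraft within 8 weeks".

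SAP 3.1.5.2 says of the eyes it sends to the Executive Committee: "Note all of these cases will have been cloudy at least once during the" period on the path.

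**The concern.** The 56-day rule is written for grafts that never work. Because the path has no closing date, it also catches an eye that was hazy but never cloudy for a year or more and then clouds briefly. That eye becomes a failure without any test of persistence and is dated to the day after surgery. An eye with the same late course and one early clear grade must stay cloudy for 90 days. Primary-endpoint status can therefore turn on a single clear-versus-equivocal grade made early in follow-up.

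At stake are:

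- the failure status of identifiable eyes;
- the failure times used in the Cox models and the proportional-hazards checks;
- the tabulation of early failures.

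SAP 8.3 carries the same methods to years 4 and 5, so the open path would run on into the extension.

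**Working it through.** **Check of the reading.** I applied rules 1a, 1b, 2a, 2b and 3 literally to the five worked examples in SAP 3.1.4, assuming visit days where none are given. All five of the SAP's dates come out: Examples 1 and 2 on day 1, Examples 3 and 4 at the first cloudy grade of the final path, and Example 5 at the regraft.

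**Constructed histories.** E = equivocal, C = cloudy, K = clear; the number is the day. Base: E7, E30, E182, E365. Rule 3 is taken to cover any regraft of an eye that is off the path.

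| History after the day-1 grade | Day 1 equivocal | Day 1 clear |
|---|---|---|
| Base, C730, C744 | Failure, dated day 1 (rule 1a) | Not a failure at day 744: 14 days cloudy, 90 needed |
| Base, C730, C744, K760, K1095 | Failure, dated day 1 | Never a failure |
| Base, E730, regraft at 900 | Failure, dated day 1 (rule 1b) | Failure, dated day 900 |
| Base, E730, E1095 | On the path, no cloudy grade | Off the path, censored |

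The second row shows a change of status. The third shows a change of date only, because a regraft counts as a failure in any case.

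**SAP 3.1.5 side by side.** The fourth row, with day 1 equivocal, is the problem case.

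- 3.1.5.2 describes eyes off the path at 3 years as clear, or equivocal following clear. An eye equivocal since day 1 is neither, so it is on the path. It goes to committee review if nothing later settles it. If it is regrafted at, say, month 38, it counts as a failure up to 3 years, dated day 1.
- A clear eye regrafted at month 38, after its 3-year visit, is censored at that visit.
- 3.1.5.1 requires at least one cloudy grade before review, and Example 5 of 3.1.5 censors an equivocal-only eye that is lost.
- The note in 3.1.5.2 is therefore untrue for this eye.

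**Size.** Inputs: 665 eyes per arm and a 4-point margin (SAP 2.0). I spread the SAP's 10% incomplete follow-up evenly over 36 months.

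- One created failure: 1/665 = 0.150 points (1/604 = 0.166 points with the uninflated sample size).
- The margin in eyes: 0.04 × 665 = 26.6.
- Re-dating a 24-month failure to day 1: the proportion uncensored at 24 months is 1 − 0.10 × 24/36 = 0.933. The contribution falls from 1/(665 × 0.933) = 0.161 to 0.150 points, a shift of −0.011.

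**How late.** In the primary analysis a failure of this kind is bounded by the 3-year visit plus data to 42 months, or to 44 months where that visit is late or absent (SAP 3.1.5.2 and 3.1.6).

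**The case against.** The strongest reply is that the SAP fills a real gap on purpose. A reader might infer that it breaches a 3-month persistence requirement in the protocol. It does not: that route covers only corneas that were initially clear, and this eye never was. It falls between the two routes. Example 1 and the cause list show that the authors meant to admit equivocal day-1 eyes, and rule 1a adds the safeguard of a second cloudy grade. This part of the reply stands. What remains is that neither document states when the day-1 path stops, and nothing explains why a first cloudy grade at two years should belong to it.

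Three further points also stand.

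- A regraft before the 3-year visit is a failure whatever the path, so rule 1b alters only its date.
- A reader might infer that a day-1 date forces the label of early or primary donor failure and so removes the eye from the endothelial-decompensation analysis in SAP 3.2.3. The SAP classifies principal cause separately and does not tie it to the date. The non-rejection category does require an initially clear stroma, so the right label for a never-clear eye is uncertain, but it is not fixed.
- Dilution of the contrast is negligible. Suppose 10 false failures arose regardless of arm among about 1,250 non-failures (1,330 less 6%, about 80). A true difference of 4.00 points would become 4.00 × (1 − 10/1250) = 3.97. The standard error would rise by about 6% (√(90/80) = 1.06), which makes non-inferiority harder to show.

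Committee review softens the 3.1.5.2 problem for unconfirmed cases. It does not reach the post-visit regraft, which counts without review.

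**Conclusion.** The point holds as a gap in the endpoint rules and a contradiction within SAP 3.1.5. For eyes equivocal on day 1 and never graded clear, 3.1.4 has no end date. 3.1.5.2 conflicts with 3.1.5.1 and Example 5 over the never-cloudy eye, and the note in 3.1.5.2 is wrong.

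The documents give no count of such eyes, and none should be inferred; the number is probably small. A created failure needs an eye that is never clear, then cloudy twice, then clear again before 90 days, or one never clear and never cloudy that is regrafted between the 3-year visit and 42 months. Each adds about 0.15 points to its arm. The rule is the same in both arms, so a reader should not infer that the non-inferiority conclusion is in danger. The effects that matter are on failure status, failure dates in the Cox analyses, and early-failure tabulations. That warrants a correction before analysis, no more.

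**What to change.** 1. In SAP 3.1.5.2, add the condition already used in 3.1.5.1: at least one cloudy grade while on the path. Apply it both to the rule on post-visit regraft or confirmation and to committee review. Censor other eyes at the 3-year visit and delete the note.
2. In SAP 3.1.4, limit the change to eyes equivocal (not cloudy) on day 1 with no cloudy grade up to and including the first graded visit on or after day 56. On the protocol schedule that is at latest the 6-month visit, if it is kept. End the day-1 path there. Later clouding follows rule 2, dated to the first cloudy grade, and a regraft with no earlier cloudy grade is dated at the regraft.

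Eyes cloudy on day 1, or at any visit up to that point, stay under rule 1. Example 1 keeps its day-1 date if its first cloudy grade is at the first visit from day 56, and Example 2 does if the regraft precedes that visit. In the first two constructed histories with day 1 equivocal, the eye is then not a failure on the grades shown. The third is dated day 900 and the fourth is censored at the 3-year visit.

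The cost is SAP wording and a few lines of endpoint code, with no new data. The downside is that a few slow early failures would be dated later, though still counted once cloudy for 90 days or regrafted.
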